Date of Issue: 10 December 2019

Covance Study ID: 000000150525

Potentially leading to amputation	10058042	Wound abscess
Potentially leading to amputation	10059245	Angiopathy
Potentially leading to amputation	10059385	Extremity necrosis
Potentially leading to amputation	10059442	Wound infection staphylococcal
Potentially leading to amputation	10059444	Wound infection pseudomonas
Potentially leading to amputation	10060734	Diabetic foot
Potentially leading to amputation	10060803	Diabetic foot infection
Potentially leading to amputation	10060963	Arterial disorder
Potentially leading to amputation	10060965	Arterial stenosis
Potentially leading to amputation	10061627	Amputation
Potentially leading to amputation	10061655	Arterial graft
Potentially leading to amputation	10061657	Arterial stent insertion
Potentially leading to amputation	10061666	Autonomic neuropathy
Potentially leading to amputation	10061815	Diabetic vascular disorder
Potentially leading to amputation	10062198	Microangiopathy
Potentially leading to amputation	10062255	Soft tissue infection
Potentially leading to amputation	10062585	Peripheral arterial occlusive disease
Potentially leading to amputation	10062599	Arterial occlusive disease
Potentially leading to amputation	10062610	Ischaemic limb pain
Potentially leading to amputation	10062932	Wound treatment
Potentially leading to amputation	10064250	Staphylococcal osteomyelitis
Potentially leading to amputation	10064601	Iliac artery occlusion
Potentially leading to amputation	10065237	Osteomyelitis bacterial
Potentially leading to amputation	10065239	Osteomyelitis fungal
Potentially leading to amputation	10065240	Wound infection bacterial
Potentially leading to amputation	10065242	Wound infection fungal
Potentially leading to amputation	10068653	Bone abscess
Potentially leading to amputation	10069379	Peripheral arterial reocclusion
Potentially leading to amputation	10072170	Skin wound
Potentially leading to amputation	10072557	Peripheral artery restenosis
Potentially leading to amputation	10072560	Peripheral endarterectomy
Potentially leading to amputation	10072561	Peripheral artery bypass
Potentially leading to amputation	10072562	Peripheral artery stent insertion
Potentially leading to amputation	10072563	Peripheral artery stenosis
Potentially leading to amputation	10072564	Peripheral artery thrombosis
Potentially leading to amputation	10074396	Penetrating atherosclerotic ulcer
Potentially leading to amputation	10075118	Subperiosteal abscess
Potentially leading to amputation	10075714	Vasculitic ulcer

Statistical Analysis Plan

Version: 3

Lexicon Pharmaceuticals Protocol No. EFC14834

Date of Issue: 10 December 2019

Covance Study ID: 000000150525

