10.3.1 Temporary treatment discontinuation with investigational medicinal product(s)

Temporary treatment discontinuation may be considered by the Investigator because of suspected AEs. Lower extremity complications (such as skin ulcers, infection, osteomyelitis, and gangrene) requiring treatment should lead to temporary discontinuation of IMP. Reinitiating treatment with the IMP will be done under close and appropriate clinical and/or laboratory monitoring once the Investigator will have considered according to his/her best medical judgment that the occurrence of the concerned event was unlikely to be related to the IMP.

It is in the interest of the patient to monitor blood glucose during the temporary discontinuation period, therefore regular determination of SMBG is to be performed and documented.

For all temporary treatment discontinuations, duration should be recorded by the Investigator in the appropriate pages of the e-CRF when considered as confirmed.

Temporary treatment discontinuation decided by the Investigator corresponds to more than 1 dose not administered to the patient.

Use of any different anti-hyperglycemic medication during the time of temporary treatment discontinuation (ie, insulin during a hospitalization) is recorded as concomitant medication with the name and doses recorded in the e-CRF.

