- ii. recorded in eCRF “Renal Event – Dialysis”,
- iii. identified as “Renal transplant” in eCRF “Other procedure”,

Renal death will be part of all deaths specified above.

Other EOSIs

For EOSIs that are not adjudicated, the number (%) of patients with at least one event will be summarized by treatment group and by PT (as identified in [Table 3](#) in [Section 2.1.4.2](#)).

Severe hypoglycemia will be included in the summary of hypoglycemia (See [Section 2.4.5.1](#)).

AE leading to an amputation is described in the section below.

Analysis of Amputation

The number (%) of patients with amputation will be summarized by treatment group and by PT and LLT during the study (ie, regardless of on- or post-treatment). Amputation is a procedure recorded in eCRF form “Other Procedures related to Amputation”. Patients who had a procedure related to amputation will be listed.

The number (%) of patients with an “AE leading to an amputation” will be summarized by treatment group and by PT. The “AE leading to an amputation” is determined by the AE identifier recorded in eCRF “Other Procedures related to Amputation” when “AE correction” is chosen as the reason for the amputation procedure.

In addition, the number (%) of patients with an “AE potentially leading to an amputation” will be summarized by treatment group and by PT (as identified in [Table 3 in Section 2.1.4.2](#)). These PTs in [Table 3](#) were requested by the European Medicines Agency (EMA)/ Pharmacovigilance Risk Assessment Committee (PRAC) Assessment Report, 9 February 2017). The associated list will be provided as well, with patients who had an amputation procedure flagged. “AE potentially leading to an amputation” represents the condition that may potentially lead to the amputation procedure, but not in all cases an amputation has occurred.

Analysis of pretreatment and posttreatment AEs

- All pretreatment AEs by primary SOC and PT, showing the number (%) of patients with at least 1 pretreatment AE, sorted by the internationally agreed SOC order and decreasing incidence of PTs within each SOC in the sotagliflozin group
- All posttreatment AEs by primary SOC and PT, showing the number (%) of patients with at least 1 posttreatment AE, sorted by the internationally agreed SOC order and decreasing incidence of PTs within each SOC in the sotagliflozin group.

Listings

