Bladder cancer	10005077	Bladder squamous cell carcinoma stage I
Bladder cancer	10005078	Bladder squamous cell carcinoma stage II
Bladder cancer	10005079	Bladder squamous cell carcinoma stage III
Bladder cancer	10005080	Bladder squamous cell carcinoma stage IV
Bladder cancer	10005081	Bladder squamous cell carcinoma stage unspecified
Bladder cancer	10005084	Bladder transitional cell carcinoma
Bladder cancer	10051690	Urinary bladder sarcoma
Bladder cancer	10057352	Metastatic carcinoma of the bladder
Bladder cancer	10066749	Bladder transitional cell carcinoma stage 0
Bladder cancer	10066750	Bladder transitional cell carcinoma recurrent
Bladder cancer	10066751	Bladder transitional cell carcinoma stage I
Bladder cancer	10066752	Bladder transitional cell carcinoma stage IV
Bladder cancer	10066753	Bladder transitional cell carcinoma stage II
Bladder cancer	10066754	Bladder transitional cell carcinoma stage III
Bladder cancer	10071664	Bladder transitional cell carcinoma metastatic
Bladder cancer	10078341	Neuroendocrine carcinoma of the bladder
Potentially leading to amputation	10003084	Areflexia
Potentially leading to amputation	10003178	Arterial thrombosis
Potentially leading to amputation	10003210	Arteriosclerosis
Potentially leading to amputation	10003222	Arteriosclerotic gangrene
Potentially leading to amputation	10006784	Burning sensation
Potentially leading to amputation	10007904	Cellulitis enterococcal
Potentially leading to amputation	10007905	Cellulitis gangrenous

COVANCE INC. CONFIDENTIAL

Statistical Analysis Plan

Version: 3

Lexicon Pharmaceuticals Protocol No. EFC14834

Date of Issue: 10 December 2019

Covance Study ID: 000000150525

Potentially leading to amputation	10007921	Cellulitis staphylococcal
Potentially leading to amputation	10007922	Cellulitis streptococcal
Potentially leading to amputation	10012174	Dehydration
Potentially leading to amputation	10012665	Diabetic gangrene
Potentially leading to amputation	10012679	Diabetic neuropathic ulcer
Potentially leading to amputation	10012680	Diabetic neuropathy
Potentially leading to amputation	10017711	Gangrene
Potentially leading to amputation	10020937	Hypoesthesia
Potentially leading to amputation	10021137	Hypovolaemia
Potentially leading to amputation	10021519	Impaired healing
Potentially leading to amputation	10021784	Infected skin ulcer
Potentially leading to amputation	10022562	Intermittent claudication
Potentially leading to amputation	10024774	Localised infection

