Potentially leading to amputation	10028862	Necrosis ischaemic
Potentially leading to amputation	10029331	Neuropathy peripheral
Potentially leading to amputation	10031149	Osteitis
Potentially leading to amputation	10031252	Osteomyelitis
Potentially leading to amputation	10031253	Osteomyelitis acute
Potentially leading to amputation	10031256	Osteomyelitis chronic
Potentially leading to amputation	10031262	Osteomyelitis salmonella
Potentially leading to amputation	10031264	Osteonecrosis
Potentially leading to amputation	10033775	Paraesthesia
Potentially leading to amputation	10034568	Peripheral coldness
Potentially leading to amputation	10034576	Peripheral ischaemia
Potentially leading to amputation	10034620	Peripheral sensory neuropathy
Potentially leading to amputation	10034636	Peripheral vascular disorder
Potentially leading to amputation	10036155	Poor peripheral circulation
Potentially leading to amputation	10036410	Postoperative wound infection
Potentially leading to amputation	10040026	Sensory disturbance
Potentially leading to amputation	10040840	Skin erosion
Potentially leading to amputation	10040872	Skin infection
Potentially leading to amputation	10040943	Skin ulcer
Potentially leading to amputation	10042343	Subcutaneous abscess
Potentially leading to amputation	10043607	Thrombosis
Potentially leading to amputation	10048031	Wound dehiscence
Potentially leading to amputation	10048038	Wound infection
Potentially leading to amputation	10049927	Dry gangrene
Potentially leading to amputation	10050473	Abscess limb
Potentially leading to amputation	10050502	Neuropathic ulcer
Potentially leading to amputation	10051548	Burn infection
Potentially leading to amputation	10052428	Wound
Potentially leading to amputation	10052949	Arterial therapeutic procedure
Potentially leading to amputation	10053692	Wound complication
Potentially leading to amputation	10053716	Wound necrosis
Potentially leading to amputation	10054044	Diabetic microangiopathy
Potentially leading to amputation	10056340	Diabetic ulcer
Potentially leading to amputation	10056418	Arterial bypass operation
Potentially leading to amputation	10056673	Peripheral sensorimotor neuropathy
Potentially leading to amputation	10057518	Peripheral artery angioplasty
Potentially leading to amputation	10057525	Peripheral artery occlusion
Potentially leading to amputation	10058041	Wound sepsis

COVANCE INC. CONFIDENTIAL

Statistical Analysis Plan**Version: 3**

Lexicon Pharmaceuticals Protocol No. EFC14834

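### The amputation-precursor term list in SAP Appendix F names four cellulitis subtypes but has no unspecified cellulitis term, so its by-arm count can be too low

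*SAP*

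**What the plan says.** SAP Section 2.1.4.2, Table 3, identifies an adverse event potentially leading to an amputation by the preferred terms in Appendix F. The table notes say that the category is not a protocol event of special interest, that health authorities require it, and that search terms will be brought to the MedDRA version in force at database lock.

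SAP Section 2.4.5.2, under Analysis of Amputation, summarises the number and percentage of patients with such an event by arm and by preferred term. It adds a listing in which patients who had an amputation procedure are flagged. It says that the category "represents the condition that may potentially lead to the amputation procedure", and that the terms were requested in an EMA/PRAC assessment report of 9 February 2017.

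In Appendix F the cellulitis rows of this group are "Cellulitis enterococcal", "Cellulitis gangrenous", "Cellulitis staphylococcal" and "Cellulitis streptococcal". There is no row for cellulitis without a qualifier.

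Protocol Section 10.3.1 treats limb infection as important in this trial. Its temporary-discontinuation rule refers to "Lower extremity complications (such as skin ulcers, infection, osteomyelitis, and gangrene" among the events concerned.

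**The concern.** The group is a search on listed preferred terms, so an event is counted only if its coded term is on the list. Cellulitis coded without a subtype is not on it. That sits oddly with the rest of the list, which counts plain terms for several neighbouring conditions, general entries such as "Skin infection", and much less specific ones such as Burning sensation, Paraesthesia and Wound. Excluding cellulitis on grounds of specificity would be hard to reconcile with those entries, and the SAP gives no other reason.

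At stake is the completeness of one safety summary. If limb infections coded simply as cellulitis were more frequent in one arm, the grouped comparison and its flagged listing would not show it.

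**Working it through.** The SAP states no count or rate for this category, so there is no figure to reproduce. The check is a reading of every row labelled Potentially leading to amputation in Appendix F.

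**Cellulitis rows.** There are four: enterococcal, gangrenous, staphylococcal and streptococcal. Three name an organism. The gangrenous form does not. Unspecified cellulitis rows: none.

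**Comparison with other conditions in the same list.**

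| Condition | Plain term listed? | Qualified forms listed |
|---|---|---|
| Osteomyelitis | Yes | acute ("Osteomyelitis acute"), chronic, salmonella, staphylococcal, bacterial, fungal |
| Wound infection | Yes | staphylococcal, pseudomonas, bacterial, fungal, postoperative |
| Gangrene | Yes | arteriosclerotic, diabetic, dry |
| Skin ulcer | Yes | infected |
| Cellulitis | No | enterococcal, gangrenous, staphylococcal, streptococcal |
| Abscess | No | limb, subcutaneous, wound, bone, subperiosteal |
| Necrosis | No | ischaemic, wound, extremity |

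Osteomyelitis and wound infection are the closest comparators, because they too are subdivided by organism, and both keep the plain term. Abscess and necrosis lack it, but their listed forms are restricted mostly by site or type, not by organism.

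**Consequence.** A patient is left out of the group if (a) the patient has an event coded as unspecified cellulitis and (b) the patient has no other event on the list. Both conditions are needed, because the summary counts patients.

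**Size.** The documents give neither quantity. As illustration only, assume that 0.5% to 3% of patients have unspecified cellulitis over the 79 weeks, that 50% to 100% of them have no other listed term, and that there are about 250 patients per arm (500 randomised 1:1).

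- Expected patients left out per arm = 250 × incidence × share not otherwise counted
- Low end: 250 × 0.005 × 0.5 = 0.6
- High end: 250 × 0.03 × 1.0 = 7.5
- Chance of at least one in an arm = 1 − (1 − incidence × share)^250
- Low end: 1 − 0.9975^250 = 0.47. High end: 1 − 0.97^250, above 0.99

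If no such events occur, nothing is left out. The range follows from the assumed inputs and is not evidence about this trial.

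**The case against.** The strongest reply is that the list is not the sponsor's own. The SAP says a regulator requested the terms, and the report is not among the documents. They cannot show whether a term was lost in transcription or the requested list was reproduced faithfully. This stands. A reader might infer a sponsor error from the gap, but the documents do not support that. Nor do they show the dictionary entry for unspecified cellulitis, so its existence as a preferred term in the version used has to be confirmed.

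A reader might also infer that every family in the list carries its plain term except cellulitis. Abscess and necrosis show otherwise, so the absence of a parent term is not in itself proof of a mistake. The argument rests on the closer comparators.

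It is tempting to say that all cellulitis recorded without an organism is missed. The gangrenous form is captured and names no organism. It is equally tempting to argue that, because the flow chart schedules no wound or skin culture, clinical cellulitis will rarely have an organism recorded. The flow chart covers routine visits. Work-up of an adverse event is separate, and Protocol Section 10.4.2 has the investigator record the additional investigations performed.

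Finally, much of the potential harm is covered elsewhere. SAP Section 2.4.5.2 tabulates all treatment-emergent events by preferred term and arm for both the 26-week and 79-week periods, and provides listings of all adverse events. Amputations, and the events that led to them, are identified from the e-CRF amputation page and not from this list. An independent blinded committee reviews amputation cases and reports to the DMC. These points stand and limit the issue. What they do not supply is a group total that counts each patient once, or a listing of these precursor events with amputation flagged, that includes unspecified cellulitis.

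**Conclusion.** The point holds as a minor one. The list omits unspecified cellulitis while keeping the plain term for osteomyelitis, wound infection, gangrene and skin ulcer, and an event coded that way would fall outside the grouped count and its flagged listing.

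A reader might go further and conclude that the count is too low. The documents do not support that. It depends on such events occurring in patients with no other listed term, and no rate is given for either. The defensible statement is that the count can be too low by an unknown amount.

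The effect is confined to one descriptive safety summary and its listing. The SAP plans no statistical testing of safety data, and the primary, secondary and ABPM analyses are untouched. The conclusion assumes that unspecified cellulitis is available as a preferred term in the MedDRA version used.

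**What to change.** Check the Appendix F list against the cited EMA/PRAC report.

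- If unspecified cellulitis was dropped in error, add it to the Potentially leading to amputation group.
- If the requested list must stand as it is, say so in the SAP, and report the group total and the listing twice: as requested, and with unspecified cellulitis added.

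The cost is one row in Appendix F or one extra summary and listing, from data already collected. The planned update to the MedDRA version at database lock does not clearly cover adding a new concept, so the change should be written into the SAP explicitly. The downside is that some of the added cellulitis will not be of the lower limb. Showing the totals with and without the term lets the reader judge how much that matters.

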Appendix G Summary of statistical analyses

EFFICACY ANALYSIS

Endpoint	Analysis population	Primary analysis	Supportive analysis	Subgroup analysis	Other analyses
Primary endpoint					
HbA1c: Change from Baseline at Week 26	ITT	ANCOVA (with missing values imputed by the retrieved dropouts & washout imputation method or by control-based copy reference MI method under MNAR assumption): treatment, randomization stratum (HbA1c / SBP at screening), and country as fixed effects, and baseline HbA1c value as a covariate	Tipping point analysis; ANCOVA (with missing values imputed by the retrieved dropouts & washout imputation method or by control-based copy reference MI method under MNAR assumption)	Subgroups: race, ethnicity, age group, gender, baseline BMI, baseline HbA1c, baseline SBP, Baseline eGFR, Duration of diabetes, and country.	Summary statistics for observed values and changes from baseline by visit. Graphical presentations for mean changes from baseline (\pm SE) and mean values (\pm SE) by visit. By-visit summary and graph excluding measurements after rescue therapy.
Secondary endpoints					
2-hour PPG, FPG, body weight: Change from Baseline to Week 26; SBP (for patients with baseline SBP \geq 130 mmHg, all patients): Change from Baseline to Week 12	ITT	ANCOVA (with missing values imputed by the retrieved dropouts & washout imputation method or by control-based copy reference MI method under MNAR assumption): treatment, randomization stratum (HbA1c / SBP at screening), and country as fixed effects, and baseline endpoint value as a covariate	No	No	Summary statistics for observed values and changes from baseline by visit. Graphical presentations for mean changes from baseline (\pm SE) and mean values (\pm SE) by visit.

Statistical Analysis Plan

Version: 3

Lexicon Pharmaceuticals Protocol No. EFC14834

Date of Issue: 10 December 2019

Covance Study ID: 000000150525

Endpoint	Analysis population	Primary analysis	Supportive analysis	Subgroup analysis	Other analyses
Proportion of patients with HbA1c <6.5%, <7.0% at Week 26	ITT	CMH method stratified on randomization strata (HbA1c / SBP at screening)	CMH method stratified on randomization strata (HbA1c / SBP at screening): excluding patients with baseline HbA1c values <6.5% (for <6.5% responders) or <7% (for <7% responders) respectively	No	By-visit summary and graphs of HbA1c responders (<6.5%, <7%). By-visit frequency summary and graphs of HbA1c responders (<6.5%, <7%) excluding patients with baseline HbA1c values <6.5% or <7% respectively.
Other endpoints					
UACR, UGE, and UGCR, serum creatinine, eGFR: Change from Baseline	ITT	Summary statistics for observed values and changes from baseline by visit.	No	No	Graphical presentations for mean changes from baseline (\pm SE) and mean values (\pm SE) by visit as appropriate.
SBP (for patients with baseline SBP <130 mmHg), DBP: Change from Baseline to Week 12		Summary statistics for observed values and changes from baseline by visit.	No	No	Graphical presentations for mean changes from baseline (\pm SE) and mean values (\pm SE) by visit as appropriate.
SBP (for all patients and patients with baseline SBP \geq 130 mmHg): Change from Baseline to Week 26		Summary statistics for observed values and changes from baseline by visit.	No	No	No
HbA1c, FPG, SBP (for all patients and patients with baseline SBP \geq 130 mmHg), body weight: Change from Baseline to Week 79		Summary statistics for observed values and changes from baseline by visit.	No	No	No

Statistical Analysis Plan

Version: 3

Lexicon Pharmaceuticals Protocol No. EFC14834

Date of Issue: 10 December 2019

Covance Study ID: 000000150525

Endpoint	Analysis population	Primary analysis	Supportive analysis	Subgroup analysis	Other analyses
Proportion of patients: achieving SBP <130 mmHg for those with baseline SBP ≥130 mmHg, achieving DBP <80 mmHg for those with baseline DBP ≥80 mmHg, with reduction in body weight by ≥2%, ≥5%, and ≥10% from baseline	ITT	By-visit frequency summary	No	No	By-visit graphical presentation as appropriate
Proportion of patients requiring rescue for hyperglycemia	ITT	Summary statistics	No	No	KM plot, List of patients rescued
ABPM Substudy		ABPM population			
Primary endpoint					
Change from Baseline to Week 12 in average 24-hour SBP in a subset of patients with SBP ≥130 mmHg at Screening	ABPM population	ANCOVA (with missing values imputed by the retrieved dropouts & washout imputation method or by control-based MI method under MNAR assumption): treatment, randomization stratum (HbA1c), and country as fixed effects, and baseline SBP value as a covariate	No	No	Summary statistics for observed values and changes from baseline by visit.
Secondary endpoint					
Average 24-hour SBP: Change from Baseline to Week 26	ABPM population	ANCOVA (with missing values imputed by the retrieved dropouts & washout imputation method or by control-based MI method under MNAR framework): treatment, randomization stratum (HbA1c), and country as fixed effects, and baseline SBP value as a covariate	No	No	Summary statistics for observed values and changes from baseline by visit.
Average 24-hour DBP, average adjusted awake time BP as measured by SBP and DBP with adjustment based on actigraphy, average adjusted sleep time BP as measured by SBP and DBP with adjustment based on actigraphy: Change from Baseline to Week 12 and 26					

Statistical Analysis Plan**Version: 3**

Lexicon Pharmaceuticals Protocol No. EFC14834

Date of Issue: 10 December 2019

Covance Study ID: 000000150525

SAFETY ANALYSES

Endpoint	Analysis Population	Primary analysis	Supportive Analysis	Subgroup analysis	Other analyses
hypoglycemia	Safety	Follow safety guidelines Number (%) of patients with any hypoglycemia, severe hypoglycemia, documented symptomatic hypoglycemia during TEAE period, and incidence rates in 100 patient-years.		Severe hypoglycemia or documented symptomatic hypoglycemia by subgroups: race, age group, gender	KM plot time to first event of severe hypoglycemia or documented symptomatic hypoglycemia Documented symptomatic hypoglycemia maybe presented by <54 mg/dL (3.0 mmol/L) as appropriate.
Adverse Events	Safety	Follow safety guidelines	No	Common TEAEs by subgroups: race, age, gender, baseline SBP, baseline eGFR	
Clinical laboratory data	Safety	Follow safety guidelines	Descriptive	No	No
Vital signs	Safety	Follow safety guidelines	Descriptive	No	No
ECG, Physical examination	Safety	Follow safety guidelines	Frequency summary	No	No

Statistical Analysis Plan

Version: 3

Lexicon Pharmaceuticals Protocol No. EFC14834

Date of Issue: 10 December 2019

Covance Study ID: 000000150525

